### **VISUAL DISTURBANCE**

Definition: Retinal and eye changes of SLE. Include cytooid bodies, retinal hemorrhages, serous exudate or hemorrhages in the choroid, or optic neuritis. Exclude hypertension, infection or drug causes.

This is scored exactly as defined with the understanding that it must be supported by objective evidence.

### **CRANIAL NERVE DISORDER**

Definition: New onset of sensory or motor neuropathy involving cranial nerves. Include vertigo due to lupus.

## **Appendix 10 Systemic Lupus Erythematosus Disease Activity Index (SLEDAI-2K) (cont.)**

This is scored exactly as defined with the understanding that it must be supported by objective evidence. However, it should be noted that hydroxychloroquine can affect the eighth cranial nerve.

### **LUPUS HEADACHE**

Definition: Severe persistent headache: may be migrainous, but must be non-responsive to narcotic analgesia.

For this descriptor to be counted, the headache must be present for greater than 24 hours and must not be responsive to narcotic analgesia. Objective documentation need not be present although it is expected that such a complaint, given the severity, would prompt formal testing such as MRI, CT, LP, etc. Furthermore, the headache should be of sufficient severity to warrant the initiation of glucocorticoids or additional immunosuppressive agents. Scoring of this descriptor means attribution of the headache to CNS lupus.

**Most headaches, including most severe and/or migrainous headaches are not attributable to lupus and this descriptor should only be scored very rarely.**

### **CVA**

Definition: New onset of cerebrovascular accident (s). Exclude arteriosclerosis or hypertensive causes.

This descriptor is scored if the patient has had a CVA within 28 days of the current encounter. A patient recovering from a CVA that was documented more than 28 days prior to the current encounter is not given points for this descriptor. A patient may have had a previous CVA but to be scored the current CVA must be new.

This descriptor is scored in the presence or absence of anti-phospholipid antibodies, i.e., the precise pathophysiologic mechanism need not be known.

The CVA is scored even in the presence of a normal CT or MRI. A TIA is also scored if the patient gives a convincing history. To exclude atherosclerosis the patient has to have a normal carotid and/or vertebral Doppler and cannot have uncontrolled hypertension.

## **Appendix 10 Systemic Lupus Erythematosus Disease Activity Index (SLEDAI-2K) (cont.)**

### **VASCULITIS:**

Definition: Ulceration, gangrene, tender finger nodules, periungual infarction, splinter hemorrhages, or biopsy or angiogram proof of vasculitis.

To score this descriptor the above definitions must be present. For example, erythematous lesions on the hands or feet which may be characteristically considered "leukocytoclastic vasculitis" but do not fulfill at least one of the above definitions and if not biopsied, are not counted. Similarly livedo reticularis is not counted. Healed ulcers with residual scar are not to be counted, but be sure to count these in the damage index. A lesion consistent with erythema nodosum should be counted regardless of whether it is biopsied or not. Purpura in the presence of a normal platelet count should be counted regardless of whether it has been biopsied or not.

### **ARTHRITIS**

Definition: Two or more joints with pain and signs of inflammation, i.e., tenderness, swelling, or effusion.

Arthritis is scored if it is ongoing; it need not be new or recurrent.

Arthritis is scored only if at least two joints manifest signs of inflammation. The rheumatologist must be convinced that this is active arthritis due to lupus.

Inflammation of the tendons, ligaments, bursae, and other periarticular structures are not scored. For example subacromial bursitis and trochanteric bursitis are not scored. If further evaluation reveals osteonecrosis or osteoarthritis, this descriptor is not counted.

### **MYOSITIS**

Definition: Proximal muscle aching/weakness, associated with elevated creatine phosphokinase/aldolase or electromyogram changes or a biopsy showing myositis.

The patient complains of muscle aching and/or weakness in the proximal muscles PLUS one of the following must be present:

1. elevated serum creatinine phosphokinase and/or aldolase
2. abnormalities on electromyogram consistent with myositis
3. biopsy-proven myositis

## Appendix 10 Systemic Lupus Erythematosus Disease Activity Index (SLEDAI-2K) (cont.)

**RENAL: Note that the following domains (urinary casts, hematuria, proteinuria, and pyuria) can only be evaluated on clean catch urinalysis specimens.**

### URINARY CASTS

Definition: Heme-granular or red blood cell casts.

This is scored if red blood cell casts are seen, even if it is only one. Pigmented casts are counted but non-pigmented granular casts, hyaline or waxy casts are not counted.

### HEMATURIA

Definition: >5 red blood cells/high power field. Exclude stone, infection or other cause.

With regard to this descriptor, every attempt should be made to see patients when they are not menstruating. If this is not possible the urinalysis should be deferred until the next visit.

This descriptor is not scored if there is documented renal calculi or infection. The latter must be confirmed by a positive urinary culture. However it is acknowledged that associated conditions such as chlamydia or urethral irritation may result in mild hematuria and the physician's best judgment is warranted. **The important point is attribution: there must be other evidence of nephritis and other causes of hematuria must be excluded.**

In the complete absence of proteinuria, attribution of hematuria to active nephritis would be very unlikely unless pathology is limited to the mesangium.

### PROTEINURIA

Definition: proteinuria of more than 0.5 g/24 hours (or equivalent by spot urine protein to creatinine ratio).

Must be attributed to active lupus nephritis.

### PYURIA

Definition: >5 white blood cells/high power field. Exclude infection.

## Appendix 10 Systemic Lupus Erythematosus Disease Activity Index (SLEDAI-2K) (cont.)

This descriptor is not scored if there is evidence of vaginal contamination (presence of any squamous epithelial cells) or a documented infection. The latter must be confirmed by a positive urinary culture. However, it is acknowledged that associated conditions such as chlamydia, trichomonas or urethral irritation may result in mild pyuria and the physician's best judgment is warranted. **The important point is attribution; there must be other evidence of nephritis, and other causes of pyuria should be excluded.** In the complete absence of proteinuria, attribution of hematuria to active nephritis would be very unlikely unless pathology is limited to the interstitium.

### **RASH**

Definition: Ongoing inflammatory lupus rash.

A rash is scored if it is ongoing, new or recurrent. Even if it is identical in terms of distribution and character to that observed on the last visit and the intensity is improved, it is counted. Therefore, despite improvement in a rash, if it is still ongoing it represents disease activity. The rash must be attributable to SLE. A description of the rash must appear in the physical exam and should include distribution, characteristics such as macular or papular, and size.

The following should not be scored:

1. Chronic scarred discoid plaques in any location.
2. Transient malar flush, i.e., it is not raised and is evanescent

A common problem one may encounter is the differentiation between scoring a lesion as "rash" and/or "vasculitis". If a lesion meets the descriptive criteria of the latter it should not also be counted as rash, i.e., the score would be 8 points not 10 points. If a separate rash characteristic of SLE is present only then would "rash" also be scored.

### **ALOPECIA:**

Definition: Ongoing abnormal, patchy or diffuse loss of hair due to active lupus.

This should be scored if any of the following conditions are present:

1. There is temporal thinning which is newly present for less than six months (if temporal alopecia is present for more than six months with no change it should not be counted)

## **Appendix 10 Systemic Lupus Erythematosus Disease Activity Index (SLEDAI-2K) (cont.)**

2. Areas of scalp with total bald spots if present for less than six months (does not need to have accompanying discoid lesion or follicular plugging)
3. The presence of "lupus frizz" i.e., short of strands of unruly hair in the frontal or temporal area

If a patient complains of hair loss and there is nothing apparent on exam this descriptor is not scored.

### **MUCOSAL ULCERS:**

Definition: Ongoing oral or nasal ulcerations due to active lupus.

An ulcer is scored if it is ongoing, it need not be new or recurrent. Ulcers can be present in either the nose or oral cavity. Erythema alone without frank ulceration is not sufficient to be scored, even if the erythema is present on the upper palate. Ulcers on the buccal mucosa and tongue are counted.

Mucosal ulcers are not counted as vasculitis.

### **PLEURISY**

Definition: Classic and severe pleuritic chest pain or pleural rub with effusion or new pleural thickening due to lupus.

This descriptor is scored if the patient complains of pleuritic chest pain lasting greater than 12 hours. The pain should be classic, i.e., exacerbated by inspiration, to help distinguish it from musculoskeletal conditions such as costochondritis, which could be confused with pleurisy. The symptom must also be accompanied by objective findings.

### **PERICARDITIS:**

Definition: Classic and severe pericardial pain with rub or effusion, or electrocardiogram or echocardiogram confirmation.

The symptom must be accompanied by objective findings.

### **LOW COMPLEMENT:**

Definition: Decrease in CH50, C3 or C4 below the lower limit of normal for testing laboratory.

## **Appendix 10 Systemic Lupus Erythematosus Disease Activity Index (SLEDAI-2K) (cont.)**

Exclude a low C4 or CH50 in patients with known inherited deficiency of C4.

### **INCREASED DNA BINDING**

Definition: >25% binding by Farr assay or above normal range for testing laboratory.

### **FEVER:**

Definition: >38°C. Exclude infectious cause.

This would be scored if one of the following conditions are present:

1. A documented temperature elevation >100.4°F or >38°C at the time of the visit.
2. A convincing history from the patient that she/he has been febrile within the preceding 10 days prior to the visit without any signs or symptoms suggestive of infection. Febrile is defined as above and not simply that the patient felt feverish. In this case the patient need not be febrile at the time of the visit for a score of 2 to be given.

As stated in the SLEDAI, fever secondary to infection is not to be scored although it is acknowledged that concomitant lupus activity and infection can occur. Fever in the presence of infection should only be scored on the SLEDAI if other evidence of lupus activity is present.

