### Systemic Lupus Erythematosus Disease Activity Index (SLEDAI-2K)

(Circle in SLEDAI Score column if descriptor is present at the time of the visit or in the preceding 4 weeks) (The same instrument can also be used going back only ten days)

Item no.	SLEDAI SCORE	Descriptor	Definition
1	8	Seizure	Recent onset, exclude metabolic, infectious or drug causes
2	8	Psychosis	Altered ability to function in normal activity due to severe disturbance in the perception of reality. Include hallucinations, incoherence, marked loose associations, impoverished thought content, marked illogical thinking, bizarre, disorganised, or catatonic behaviour. Exclude uraemia and drug causes
3	8	Organic brain syndrome	Altered mental function with impaired orientation, memory, or other intellectual function, with rapid onset and fluctuating clinical features, inability to sustain attention to environment, plus at least 2 of the following: perceptual disturbance, incoherent speech, insomnia or daytime drowsiness, or increased or decreased psychomotor activity. Exclude metabolic, infectious or drug causes
4	8	Visual disturbance	Retinal changes of SLE. Include cytoid bodies, retinal hemorrhages, serous exudates or hemorrhages in the choroid, or optic neuritis. Exclude hypertension, infection, or drug causes
5	8	Cranial nerve disorder	New onset of sensory or motor neuropathy involving cranial nerves
6	8	Lupus headache	Severe, persistent headache; may be migrainous, but must be non-responsive to narcotic analgesia THIS WOULD RARELY BE ATTRIBUTED TO SLE...ALMOST NEVER SCORED
7	8	CVA	New onset Cerebrovascular accident(s). Exclude arteriosclerosis
8	8	Vasculitis	Ulceration, gangrene, tender finger nodules, periungual infarction, splinter hemorrhages or biopsy or angiogram proof of vasculitis
9	4	Arthritis	>= 2 joints with pain and signs of inflammation (i.e. tenderness, swelling or effusion)
10	4	Myositis	Proximal muscle aching/weakness, associated with elevated creatinine phosphokinase (CK)/aldolase, or EMG changes or a biopsy showing myositis
11	4	Urinary casts	Heme-granular or RBC casts
12	4	Hematuria	> 5 RBC/high power field. Exclude stone, infection or other cause
13	4	Proteinuria	> 0.5 gram/24 hours
14	4	Pyuria	> 5 WBC/high power field. Exclude infection
15	2	Rash	Inflammatory type rash
16	2	Alopecia	Abnormal, patchy or diffuse loss of hair

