**Appendix 10**  
**Systemic Lupus Erythematosus Disease Activity Index**  
**(SLEDAI-2K) (cont.)**

Item no.	SLEDAI SCORE	Descriptor	Definition
17	2	Mucosal ulcers	Oral or nasal ulcerations
18	2	Pleurisy	Pleuritic chest pain or pleural rub with effusion, or pleural thickening (requires objective evidence)
19	2	Pericarditis	Classic pericardial pain and/or rub, effusion with ECG or echocardiogram confirmation (requires an objective component)
20	2	Low complement	Decrease in CH50, C3 or C4 below lower limit of normal for testing laboratory
21	2	Increased DNA binding	Increased DNA binding above normal range for testing laboratory
22	1	Fever	> 38°C. Exclude infectious cause
23	1	Thrombocytopenia	< 100 x 10  platelets/L, exclude drug causes
24	1	Leukopenia	< 3 x 10  WBC/L, exclude drug causes

SCORE:

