## **Appendix 10 Systemic Lupus Erythematosus Disease Activity Index (SLEDAI-2K) (cont.)**

### **GUIDELINES FOR USE OF SLEDAI-2K MODIFIED FOR ASSESSMENT OVER 28 DAYS: TO ASSESS DISEASE ACTIVITY**

#### **General guidelines for filling out the SLEDAI-2K:**

- The main principle to keep in mind is that this instrument is intended to evaluate current lupus activity and not chronic damage, severity is accounted for in part by the "weightedness" of the scale.
- Points are given exactly as defined.
- A descriptor is either scored the exact points allotted or not scored, i.e. given a zero. Descriptors are scored only if they are present at the time of the physician encounter or in the preceding 28 days. Windows acceptable in a clinical trial are acceptable in scoring the SLEDAI. However, it is never acceptable to fill in gaps which cover activity over 2-3 months or more. The reason for this is that disease activity at the visit might have changed several times in such intervals and the recording of distant activity becomes meaningless.

Please note that in the original SLEDAI the disease activity being scored was meant to cover only a ten day period, the modification to 28 days is a more useful assessment for use in clinical trials, in order to capture disease activity between monthly visits.

- The descriptor must be documented by the notes written in the physician encounter form and generally applies to the clinical data and not to the laboratory data. The laboratory data is strictly defined as per cutoffs and documentation is provided by the reports from the commercial laboratory.
- Descriptors do not have to be new but can be. They can be ongoing, recurrent, or initial events. Each would be scored the same way. An example would be a malar rash or mucosal ulcer. In these situations a malar rash observed at the initial visit but which remains unchanged for the next six months, irrespective of any treatment, is scored 2 points each time the SLEDAI is completed. Since the nature of lupus is that manifestations are not usually fleeting it would be rare for descriptors to appear transiently during the month and not at the time of the encounter. This is discussed in more detail for each descriptor but is especially relevant for the neurologic (except for seizure or CVA), pulmonary, and cutaneous manifestations.

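### Fever in the SLEDAI-2K is worth 1 point in the scoring table but 2 in the rater guideline; two Damage Index glossary lines also contradict the amended table

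*Combined protocol and SAP*

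**What the plan says.** Protocol Appendix 10 holds both the SLEDAI-2K scoring table and a guideline for raters. In the table, item 22 is fever, weight 1, defined as "> 38°C. Exclude infectious cause". The header above the table instructs: "Circle in SLEDAI Score column if descriptor is present at the time of the visit or in the preceding 4 weeks". The general guidelines in the same appendix add: "A descriptor is either scored the exact points allotted or not scored, i.e. given a zero".

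The fever entry of the guideline offers two routes: a raised temperature documented at the visit, or a convincing history from the patient. Under the second it states: "In this case the patient need not be febrile at the time of the visit for a score of 2 to be given".

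The SLEDAI-2K total is then used for:
- entry, at least 8 at screening (Section 4.1.1);
- the disease-activity stratum, cut at 10 (Section 3.3.6.5);
- SRI-4, which needs a fall of at least 4 and is the primary endpoint at Week 48 (Sections 4.5.8.9 and 6.4.1);
- SRI-6, a secondary endpoint (Section 6.4.2).

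Appendix 7 has a similar conflict. The amendment rationale adopts the 1997 version of the SLICC/ACR Damage Index. The table is labelled with a 1997 source. It scores proteinuria at or above 3.5 g/24 h, and pulmonary resection when done for malignancy. The glossary that follows is labelled with a 1996 source. It describes proteinuria below 3.5 g/24 h, and resection for reasons other than malignancy. Change in this index is an exploratory endpoint (Section 6.4.3).

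**The concern.** One item of the instrument behind eligibility, stratification and the primary endpoint has two weights in the same appendix. The difference is a single point, but every use of the total has a hard cut-off, so one point can move a patient across it. The general rule shows which weight the appendix supports, yet the rater also holds an item-level instruction that says otherwise. If sites differ in which text they follow, the same clinical picture produces different totals.

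The Damage Index lines matter less. Each glossary line points the opposite way from the table it is meant to explain, but only an exploratory endpoint depends on them.

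**Working it through.** **Inputs.** Table weights in Appendix 10: items 1–8 score 8, items 9–14 score 4, items 15–21 score 2, items 22–24 score 1. The plan states no total. The weights sum to 8×8 + 6×4 + 7×2 + 3×1 = 64 + 24 + 14 + 3 = 105, and to 106 if fever is 2. The cut-offs are those of Sections 4.1.1, 3.3.6.5 and 4.5.8.9. The SRI-6 component is taken as a fall of at least 6, by analogy with the definition given for SRI-4.

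**Formulas.** Let S be the sum of all items other than fever, d the net fall in those items from baseline to Week 48, and w the fever weight. With fever present, the total is S + w. If fever is scored at baseline and absent at Week 48, the fall in the total is d + w.

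| Use | Rule | Other items | w = 1 | w = 2 |
|---|---|---|---|---|
| Entry | total ≥ 8 | S = 6 | 7, fails | 8, passes |
| Stratum | ≥ 10 or < 10 | S = 8 | 9, lower | 10, upper |
| SRI-4 component | fall ≥ 4 | d = 2 | 3, not met | 4, met |
| SRI-6 component | fall ≥ 6 | d = 4 | 5, not met | 6, met |

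These values are reachable. Of the 24 items, 21 have even weights, so without thrombocytopenia or leukopenia S is even. For example, arthritis (4) plus rash (2) gives S = 6.

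**Direction.** Flips can go either way. If fever is absent at baseline and scored at Week 48, the fall is d − w. With d = 5 that is 4 under the table and 3 under the guideline, so the SRI-4 component is met only under the table.

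**Two readings of the 2.** It is written under the history route, but it can also be read as the value of fever by either route. The choice decides further cases. Take fever by history at baseline, fever documented at Week 48, and d = 3. The table gives 3 + 1 − 1 = 3. The history-only reading gives 3 + 2 − 1 = 4, a flip. The general reading gives 3 + 2 − 2 = 3, no flip. Conversely, documented fever that clears, with d = 2, flips only under the general reading.

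**Conditions.** Each row is necessary, not sufficient. SRI-4 also needs the BILAG and Physician's Global Assessment criteria, and entry needs all the other criteria.

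**Damage Index, side by side.** The table's words on resection for malignancy are in italics, which the amendment rationale uses for substantive new text. The glossary's gastrointestinal and musculoskeletal entries lack pancreatic insufficiency and tendon rupture, the two items the amendment names. Both facts suggest that the table was updated and the glossary was not. Read literally, the glossary's proteinuria line would count even normal urine protein as damage.

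**The case against.** The strongest reply is that Appendix 10 already settles the matter. The printed score column offers only 1 for fever, the header tells raters to use that column, and the general rule forbids any other value. Section 4.5.8.2 plans rater training, and Appendix 3 has the Medical Monitor review every patient before enrollment. Much of this stands: it makes a wrong score unlikely. It does not remove the conflict. Adjudication is described only before enrollment, not for the Week 48 score. Section 6 leaves instrument scoring to a Data Analysis Plan that is not among these documents, so whether it limits item 22 to 0 or 1 cannot be seen.

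A reader might infer a second error from the fever look-back. The history route counts fever "within the preceding 10 days prior to the visit without any signs or symptoms suggestive of infection", while the general guideline says: "Descriptors are scored only if they are present at the time of the physician encounter or in the preceding 28 days". The documents do not show this to be a mistake. Ten days lies within 28. The table header says: "The same instrument can also be used going back only ten days". The general guideline also says of timing: "This is discussed in more detail for each descriptor", although it stresses neurologic, pulmonary and cutaneous items there. The shorter period may be a deliberate limit for fever.

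On the Damage Index, it is fair to say that the 1997 source is not available here, that a trained rater would probably see the proteinuria line as a misprint, and that scoring change from baseline cancels most earlier resections. The index also requires damage lasting 6 months. These points limit the effect, but the two lines still contradict the table.

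**Conclusion.** The conflict is real and minor. Under the appendix's own general rule, 2 is never a permitted fever score, so the guideline is wrong as written. This rests on the current text alone.

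Its size is one point on the total, and it matters only for a patient with fever who sits at a cut-off and meets all other criteria. With no fever rate in the documents, the number affected cannot be computed; it is probably very small.

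Two stronger readings are not supported. One is that the treatment comparison is biased: nothing in the documents ties such scoring errors to an arm, and flips occur in both directions, so the effect is noise. The other is that the affected cases can be listed completely or confined to fever by history: that depends on which reading of the 2 a rater adopts, and the text allows both. The four cases in the table above are illustrations. The SLEDAI-2K total or its change also enters BICLA (Section 4.5.8.10) and the flare index (Appendix 11).

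The two glossary contradictions are also real, but they bear on an exploratory endpoint only, and no size is claimed for them.

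**What to change.** - In the fever entry of the Appendix 10 guideline, change the score from 2 to 1.
- Have the scoring program accept only 0 or 1 for item 22, and say so in the Data Analysis Plan if it does not already.
- In the Appendix 7 glossary, reconcile the proteinuria and pulmonary resection lines with the table adopted by the amendment.
- Tell raters about these corrections in a short note.

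The cost is one digit in Appendix 10, two lines in Appendix 7, a rater note and one programmed check. No endpoint, visit or data is lost.
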